This study is designed to compare the efficacy of intravenous N-acetylcysteine compared to normal treatment in patients with acute ischemic stroke. Secondly, we will also look at whether there was any benefit or harm to the subjects over the time course of the study.

6) Background

Stroke is a leading cause of death and long-term disability in the United States, affecting more than 795,000 individuals annually (1). Of these, about 87% are ischemic strokes. In properly selected patients, intravenous recombinant tissue plasminogen activator (t-PA) has been shown to improve functional outcomes if given within 4.5 hours of the onset of stroke symptoms (2, 3). Endovascular treatment both via clot retrieval devices and catheter directed t-PA has demonstrated benefit in well-selected patients with a large vessel occlusion and significant salvable tissue, also known as the penumbra (4-6). For patients who are not candidates for treatment with t-PA or mechanical thrombectomy, current treatment is centered on supportive care.

N-Acetylcysteine (NAC) is an FDA approved medication that has been used successfully for many years in the treatment of acute acetaminophen overdose (79). It is generally well tolerated with the exception of rare anaphylactoid type reactions to the intravenous formulation (10, 11).

In mouse studies, N-acetylcysteine (NAC) has led to an increase in glutathione levels in the neurons along with a reduced number of microbleeds in ischemic models (12). NAC treated rats have been demonstrated to have increased level of glutathione in the astrocytes which provides a neuroprotective effect. This reduced the number of microbleeds and prevented further thrombosis or infarct (12). The efficacy of NAC by scavenging of ROS and increasing mitochondrial activities has been shown to reduce noise-induced hearing loss in chinchilla models (13). Another study on transient cerebral ischemia rat models defined a new pharmacokinetic in which the neuroprotective effects of NAC are mediated

by the increased protein levels of hypoxia-induced factor 1 (HIF-1), its target erythropoietin (EPO) and glucose transporter (GLUT-3) (14).

Studies have shown consistent, similar results for ischemic brain injury in rat (12, 15-17). Consistent human studies showing neuroprotective effects which lead to reduced symptoms after traumatic brain injury, reduced noise-induced hearing loss and as a treatment for Parkinson's disease (18-20).

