The FDA has reviewed the study and gave an FDA IND (#145,538). Approved was also given by the research divisions of Cumberland Pharmaceuticals (Cumberland Pharmaceuticals have agreed to donate N-acetylcysteine for the study).

10) Study Design

1) The treating ED physicians (other than the investigator or coinvestigators) will identify potential subjects in the Emergency Department at Harbor UCLA via initial evaluation (standard of care) including blood draw for a standard CVA panel (CBC, Chemistries, PT, PTT, neuronal specific enolase, s100b) and brain imaging. Subjects who present with neurological deficits consistent with stroke without hemorrhage less than 24 hours since symptom onset will be asked to whether they would be interested in participation in a research in our study and if so, the treating ED physician will contact investigators or study team member. Investigators or study team member may access medical record to confirm eligibility before approach subject.

If treating physician is member a co-investigator/ study team member, s/he will approach subject about participation once deemed to meet eligibility criteria. (See inclusion and exclusion criteria below). Informed consent will be obtained for all subjects either from the subjects themselves or if they do not have capacity, from their legally authorized representative (See Section 16 below).

2) Each subject will undergo, as part of standard of care, evaluation and assessment using the National Institutes of Health Stroke Scale (NIHSS) and the Modified Rankin Scale (MRS) which have been similarly used in the European Cooperative Acute Stroke Study III, ECASS III (3). The NIHSS is a 15-item scale that measures the level of neurologic impairment. The MRS is a measure of disability with scores ranging from 0 (no symptoms at all) to 6 (death). Individuals must have an NIHSS of at least 5 to be eligible for this study. This data will be recorded for study purposes using a standard data collection sheet.

3) Subjects will receive standard of care with the study intervention being considered an “add-on” therapy. Thirty minutes after enrollment, eligible subjects will be randomized into one of two arms: placebo or NAC.

PROTOCOL TITLE: Randomized Placebo Controlled Trial of Intravenous N-Acetylcysteine for the Treatment of Acute Ischemic Stroke

Any patient receiving t-PA who enrolls in the study will have their study drug infusion delayed by 24 hours after the completion of the t-PA infusion.

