Our patients tend to be economically disadvantaged but since there are no financial incentives either for the patient or for the investigators, this bias has been minimized. Patients will receive the same care whether they participate in the study or decline.

Exclusion Criteria:

- Evidence of hemorrhagic stroke on initial CT scan
- Need for thrombectomy as determined by the treating neurologist
- Known allergy to NAC
- Protected populations, including age < 18, known pregnancy, and prisoners
- Patients who are DNR/DNI at the time of presentation with a short life expectancy

b) Local Number of Subjects

The total number of local subjects will be 117 (39 subjects with moderate stroke = NIHSS 5-15; 39 subjects with moderate to severe stroke = NIHSS 16-20; 39 subjects with severe stroke = NIHSS = 21-42)

This number was derived using a group size analysis based on previous work on oral NAC for ischemic stroke (37) and a hypothesis of finding no

difference (defined as a change in NIHSS < 4) between NIHSS scores at 90 days. With a power of 0.80 and an alpha 0.05 we would need 47 subjects in each group. Assuming a dropout rate of 25% or lost to follow-up, we would enroll 59 in each group for a total of 117.

(Group sample sizes of 47 and 47 achieve 81% power to detect a difference of 4.0 using a one-sided Mann-Whitney U or Wilcoxon Rank-Sum test assuming that the actual data distribution is normal when the significance level (alpha) of the test is 0.05 and the standard deviation is 7.4 in both groups.)

c) Study-Wide Number of Subjects

This is a single center study at the Harbor-UCLA Medical Center.

d) Study Timelines

Estimated time to complete enrollment is December 2025. Review of the neurology services revealed that Harbor-UCLA typically sees 20 patients per month that would be eligible for the study.

e) Study Endpoints

The primary study endpoint will be comparison between groups (NAC treated group versus treatment) of the NIHSS at 90 days.

Secondary endpoints include changes in the MRS, GOS, BI, and blood tests at 30 days and 90 days, as well as MRI data including changes in brain volume and gliosis at 90 days.

f) Procedures Involved in the Human Research

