First, subjects will be screened for neurological deficits consistent with cerebral vascular accident via history, physical examination and emergent evaluation in the Emergency Department which will include a noncontrast CT of the brain and an emergent Stroke Code, where our Neurology team will immediately consult on the patient at the bedside.

As part of the initial evaluation, the patient will be assessed with the National Institutes of Health Stroke Scale (NIHSS) which uses a 15-item scoring system to assess the level of neurological impairment. The items assessed include: Level of consciousness (LOC) responsiveness, LOC questions, LOC commands, best gaze, visual field, facial palsy, best motor arm, best motor leg, limb ataxia, sensory function, neglect, dysarthria, best language, extinction and inattention, formerly called neglect (31, 32).

PROTOCOL TITLE: Randomized Placebo Controlled Trial of Intravenous N-Acetylcysteine for the Treatment of Acute Ischemic Stroke

A Modified Rankin Scale (MRS) will also be obtained; The MRS is a simple scoring system that runs from 0-6, from perfect health without symptoms to death. 1- no significant disability, able to carry out all usual activities, despite some symptoms. 2 - slight disability, able to look after own affairs without assistance, but unable to carry out all previous activities. 3 - moderate disability, requires some help, but able to walk unassisted. 4 - moderately severe disability, unable to attend to own bodily needs without assistance, and unable to walk unassisted. 5 - severe disability, requires constant nursing care and attention, bedridden, incontinent.

The neurology consult team in conjunction with the Emergency Department will then make an assessment as to whether the patient is eligible to receive treatment with t-PA (based on national criteria of the American Heart Association and American Stroke Association - https://www.stroke.org/-/media/Stroke-Files/Ischemic-StrokeProfessional-Materials/AIS-Toolkit/AIS-Professional-EducationPresentation-ucm_485538)

NAC or placebo infusion will be started 30 minutes after the enrollment of the study. For subjects who receive t-PA, NAC or placebo infusion will be started 24 hours after the conclusion of the t-PA infusion.

Prior to the starting of the study medication, all subjects will receive 12.5 mg intravenous diphenhydramine to reduce the incidence of allergic reactions.

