If subject is deemed incapable of decision-making or unable to physically sign a consent document, consent will be sought from the subject’s the Legally Authorized Representative (as per HRP-013 SOP LARs, Children, Guardians). This individual will complete the Self-Certification of Surrogate Decision Makers form (Appendix 3) for documentation.

Study participation will be discussed with both the patient and the physician of record/primary medical providers. Patient capacity to make decisions will be determined by the primary medical providers per routine. The study team will also determine each patient’s (potential subject’s) decision making capacity for participation in the study. Patients without capacity to make decisions and who lack a surrogate decision maker will be excluded from the study. Surrogate decision makers will be informed about the study in the same way as described above and offered to provide consent for the patient to enroll in the study.

If and when a subject regains their capacity for decision-making, consent for continued participation in the study will be sought. The standard operating procedure for informed consent will be followed (SOP: Informed Consent Process for Research, HRP-090).

17) Process to Document Consent in Writing

We are following “SOP: Written Documentation of Consent (HRP-091).”

Individuals who are not yet adults, pregnant women, and prisoners will be excluded in this study. Other vulnerable subjects, such as students, subjects with limited or no treatment options, and socially and economically disadvantaged, may be included in this study. This study does not involve more than minimal risk to the subject.

18) Drugs or Devices

N-Acetylcysteine and placebo. Study drugs will be stored, handled and dispensed by an ED pharmacist who is working at the time of study enrollment.

[name]., the ED Pharmacist will maintain drug accountability logs in compliance with FDA regulations. She will instruct other ED pharmacists about the study and the randomization log which will

be kept in the pharmacy room in the ED. She will also create study drug labels to keep the nurses, physicians and patients blinded to the study medication.

19) Multi-Site Human Research

N/A

20) Community-Based Participatory Research

This is not a community-based participatory research project.

21) Sharing of Results with Subjects

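### t-PA is prognostic by the protocol's own account and sets when study drug starts, but the only primary test named is not stratified by it; the possible shift is modest and the remedy nearly free

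*Combined protocol and SAP*

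**What the plan says.** Section 6 (Background) says that t-PA, in properly selected patients, "has been shown to improve functional outcomes if given within 4.5 hours of the onset of stroke symptoms". Patients who receive it may enrol. Section 10 f (Procedures) gives two study-drug schedules. Without t-PA: "NAC or placebo infusion will be started 30 minutes after the enrollment of the study". With t-PA: "For subjects who receive t-PA, NAC or placebo infusion will be started 24 hours after the conclusion of the t-PA infusion". Section 10, item 3, agrees: such a patient "will have their study drug infusion delayed by 24 hours after the completion of the t-PA infusion".

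The same item describes randomisation only in these words: "eligible subjects will be randomized into one of two arms: placebo or NAC". Section 18 adds that the emergency department pharmacy keeps a randomisation log. Neither place names a stratification factor or block scheme.

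On analysis, section 10 e says "The primary study endpoint will be comparison between groups (NAC treated group versus treatment) of the NIHSS at 90 days". The only test named is in the sample-size text of section 10 b: a one-sided rank-sum test with no stratum or covariate. The enrolment caps of 39 per NIHSS band (sections 2 and 10 b) control the severity mix. They do not concern t-PA and are not described as randomisation strata. The per-protocol set in section 10 f, item 7, removes stroke mimics only.

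**The concern.** Two subjects with the same enrolment NIHSS can differ in expected day-90 NIHSS because one received t-PA. If the arms end up with different t-PA shares, part of the observed difference in NIHSS reflects t-PA. The plan names no analysis that would remove that part. Someone who saw such a gap in the baseline table would have to rely on a post hoc adjustment, which is open to challenge.

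The gap is avoidable. Section 10 f places the t-PA decision in the initial emergency assessment, before study drug starts, so t-PA status should usually be known at allocation and can validly serve as a stratum.

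The later start in t-PA subjects is a separate matter. It could make the NAC effect differ by t-PA status, and the plan states no breakdown that would show this.

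**Working it through.** **Inputs from section 10 b.** Difference 4.0 points, SD 7.4, 47 evaluable per arm, one-sided alpha 0.05, stated power 81%, total enrolment 117 (about 59/58).

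**Assumed inputs.** The documents give neither the t-PA share nor its effect on day-90 NIHSS. The share p is taken as 10-40% and the effect e as 1-4 points lower NIHSS.

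**1. The plan's own figure.** The rank-sum test has efficiency 3/π against the t-test on normal data, so the effective n is 47 × 3/π = 44.9 per arm. The standard error is 7.4 × √(2/44.9) = 1.56, and 4.0/1.56 − 1.645 = 0.92, which gives 82% power. A noncentral-t calculation gives 81.5% and a simulated rank-sum test 81.7%. The stated 81% is reproduced.

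**2. Yardstick.** The standard error of the mean difference is 7.4 × √(2/47) = 1.53 points. One-sided significance needs 1.645 × 1.53 = 2.51 points.

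**3. How large an imbalance is plausible.** Among all 117 enrolled (hypergeometric, 59/58):

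| t-PA subjects | Chance of a gap of 10 points or more | 95% limit of gap |
|---|---|---|
| 18 (15%) | 13% | 13 points |
| 35 (30%) | 23% | 16 points |
| 47 (40%) | 26% | 18 points |

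Among 47 evaluable per arm (binomial), the SD of the gap is √(2p(1−p)/47):

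| Share p | SD of gap | Chance of a gap of 10 points or more |
|---|---|---|
| 10% | 6.2 points | 12% |
| 20% | 8.3 points | 25% |
| 30% | 9.5 points | 31% |
| 40% | 10.1 points | 34% |

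**4. Shift in the primary difference.** Shift = gap × e.
- A 16-point gap with e = 3 gives 0.16 × 3 = 0.48 point. That is 0.48/1.53 = 0.31 standard errors, or 12% of the 4-point target.
- The 95% limit is 1.96 × SD of gap × e. It is 0.12 point at p = 10%, e = 1; 0.37 at p = 30%, e = 2; and 0.79 at p = 40%, e = 4. The last is about half a standard error.

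**5. Error rates given an imbalance.** Take p = 30% and a 15-point gap. The residual SD is √(7.4² − e²p(1−p)), multiplied by √(2/47) for the standard error. For e = 4 this is √(54.76 − 3.36) × 0.206 = 1.48. With the gap favouring NAC, the one-sided error is P(Z > (2.51 − 0.60)/1.48) = 9.8%. These are normal approximations for the mean difference.

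| e | Type I error, gap favours NAC | Type I error, gap favours placebo | Power, gap favours NAC | Power, gap favours placebo |
|---|---|---|---|---|
| 2 | 7.2% | 3.2% | 88% | 78% |
| 4 | 9.8% | 1.8% | 92% | 73% |

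**6. Error rates averaged over randomisations.** In 4,000-run simulations (shares 20-30%, effects 2-4) with simple randomisation, the unadjusted rank-sum test kept type I error at about 5% and power at about 81%. A simulated van Elteren test changed power by about −1 to +3 points, with a gain only when the t-PA effect is about 3 points or more.

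**7. The delay.** It applies to NAC and placebo alike, so it adds no bias. It could dilute the effect. If late NAC did nothing in t-PA subjects, the average effect would be 4 × (1 − p), which is 3.6 points at p = 10% and 2.4 at p = 40%, with power of 75% and 46%. If half the effect remained, power would be 79% and 66%.

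**8. Can the trial compare the two groups?** At p = 30%, about 14 t-PA and 33 non-t-PA subjects per arm are evaluable. The standard error of the difference between the two subgroup effects is 7.4 × √(2/14 + 2/33) = 3.3 points, with 95% limits of about ±6.5. It cannot.

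**The case against.** The strongest reply is that randomisation already covers chance imbalance in any one factor. The test's error rate averages over such imbalances, and a shift of 0.3 standard errors changes only borderline results. This stands. A reader might infer that a null or positive result could not be told apart from the effect of t-PA. The documents do not support that: with a significance threshold of about 2.5 points, no shift in the assumed range comes near to producing a result alone.

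A reader might also infer that late dosing biases the comparison. It does not, because section 10 f gives both arms the same delay. Nor is early versus late dosing a clean split by t-PA: subjects without t-PA may present up to 24 hours after onset, so onset-to-drug times can overlap.

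The inputs are also open to challenge. Section 6 reports a treatment effect of t-PA in properly selected patients. That recipients here will have lower day-90 NIHSS than non-recipients, who differ in selection and arrival time, is an inference. This is why a range of effects is shown.

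Finally, omitting a stratum is a common choice, and the missing t-PA stratum is part of a thinly described randomisation and analysis. That is true, but it does not answer the conditional error rates above. The remedy uses a factor already known and needs no new data.

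**Conclusion.** The point holds as a low-cost improvement. In the text available, t-PA enters neither the allocation nor the primary test, although the protocol treats it as affecting outcome. If t-PA is unbalanced, the day-90 difference shifts by an amount whose 95% limit is below 0.8 point for shares of 10-40% and effects of 1-4 points, against a standard error of about 1.5. Given a 15-point gap at a 30% share, one-sided type I error would lie between about 2% and 10%, depending on direction and on an effect of 2 or 4 points. Averaged over randomisations it stays near 5%.

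This is a matter of conditional bias and precision and does not invalidate the trial. It rests on the assumed t-PA shares and effects, and on t-PA status usually being settled before allocation. Possible dilution of the NAC effect by the delay is a separate question of interpretation, which stratifying the test does not resolve.

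**What to change.** Before unblinding, state in section 10 e that the primary comparison of day-90 NIHSS is a rank-sum test stratified by t-PA yes/no (van Elteren), with the stratum defined by the t-PA decision made before allocation. Report the arm difference separately for t-PA and non-t-PA subjects, labelled descriptive, and say that the trial is too small to test whether the two groups respond differently.

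Stratify the allocation list by t-PA only if randomisation has not begun. The documents do not say whether it has; version 1.6 is dated October 2023 and enrolment is expected to finish by December 2025. If it has begun, keep the list and change only the analysis.

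The cost is a few lines of text, with no extra patients, visits or change in sample size. There is no power gain, and possibly a loss of up to about 1 point, if t-PA proves weakly prognostic. Cells become sparse if t-PA use is low: at a 15% share, 18 subjects spread evenly over three severity bands is six per band, or about three per arm.

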4) Subjects will be contacted by telephone 24 hours post discharge, 3 days post discharge, and at 7 days to be monitored for adverse events and asked whether they have had any new symptoms or problems since the last study assessment. This will be an open question that will be recorded prospectively for each subject. If the subject reports an adverse event this is still present at the time of the phone call and wants to be further evaluated, they will be told to return to the emergency department and seen by a physician not associated with the investigation. Further the investigator from

PROTOCOL TITLE: Randomized Placebo Controlled Trial of Intravenous N-Acetylcysteine for the Treatment of Acute Ischemic Stroke

the team will also meet them in the Emergency Department to detail the information. All adverse events, whether they are deemed mild or serious, will be forwarded immediately to the Medical Monitor who will have discretion on whether to halt the study or continue. The Medical Monitor's reports will be forwarded to the Institutional Review Board (IRB). In addition, all unanticipated problems pose a risk to subjects or others will be reported to the Institutional Review Board (IRB) as required by FDA regulations. (There is no sponsor for this study, so no report needs to go to a sponsor).

4) Subjects will be instructed to return to the neurology clinic on day 30 and day 90 for re-evaluation. The same assessment will be performed as on day zero: the NIHSS and the MRS as well as the Glasgow Outcome Scale (GOS) and Barthel Index (BI). The GOS is a 5-point scale on which 5 indicates independence and 1 death. The BI assesses the ability to perform activities of daily living, on a scale that ranges from 0 (complete dependence on help with activities of daily living) to 100 (independence). These scores will be recorded on a standard data collection sheet. A representative from the neurology department will perform the examination, blinded from the previous scoring and treatment. In addition to the neurologic evaluation, patients will be queried at this time as to whether they experienced any nausea, vomiting, flushing, and itchiness, wheezing or difficulty breathing between the time of their discharge and the reevaluation.

For convenience, the 30 day follow up will have a tolerance range +/- 3 days and the 90 day follow up will permit +/- 10 day window.

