assessment. This will be an open-ended question that will be recorded prospectively for each subject. If the subject reports an adverse event this is still present at the time of the phone call and wants to be further evaluated, they will be asked to return to the emergency department and seen by a physician not associated with the investigation. Further the investigator from the team will also meet them in the Emergency Department to detail the information. All adverse events, whether they are deemed mild or serious, will be forwarded immediately to the Medical Monitor who can immediately halt or terminate the study. In addition, all adverse events will be reported to the IRB of the Lundquist Institute by the investigators (and independently by the Medical Monitor). In a written IND safety report, any adverse experience associated with the use of the drug that was both serious and unexpected will be immediately reported to the FDA.

Definition of adverse events for this protocol:

Adverse Events

Symptoms that are new or unexpected reported by the subject

Nausea, diaphoresis, chest pain, abdominal pain, paresthesias, headache, visual complaints

Cough, pruritis, rash

Laboratory abnormality

Minor bleeding from gums, nares

Mild Sedation

Serious Adverse Events

Significant adverse events that led to an intervention, including withdrawal or dose reduction in the investigation drug or the need for concomitant therapy

Wheezing, bronchospasm, angioedema requiring rescue medications

Bleeding requiring an intervention

Hemorrhagic conversion of the ischemic CVA

Worsening neurologic condition as measured by the NIHSS at 4 hour intervals after enrollment in the study (or sooner as dictated by the care of the neurology team)

Laboratory abnormality requiring intervention (e.g. severe hyponatremia or hyperkalemia)

Death

k) Withdrawal of Subjects

Subjects will be withdrawn if they leave AMA/elope during their initial hospitalization or do not complete their 30 day or 90 day follow up prior to completion of the study

11) Risks to Subjects

Risk of N-Acetylcysteine:

Most adverse drug reactions that have been reported are minor and easily managed. Serious anaphylactoid reactions are extremely rare (11, 33-36)

Common: Nausea, vomiting, flushing, and pruritus,

Uncommon: Wheeze and bronchospasm (7.1%) Rare:

Angioedema, and hypotension (25-28)

Risks of Diphenhydramine

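### After the 7-day call the open adverse-event question is dropped, and the only one written for days 30 and 90 lists six infusion-reaction symptoms, so late bleeding and events treated elsewhere may be missed

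*Combined protocol and SAP*

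**What the plan says.** **In hospital.** Section 10, item 3, and section 10(j) have investigators ask every four hours about the infusion-reaction symptoms. At the same times they ask an open question about anything new. Item 3 gives the reason for the open question: to pick up events that are unexpected or not typical of NAC.

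**Telephone calls (section 10, first item 4).** "Subjects will be contacted by telephone 24 hours post discharge, 3 days post discharge, and at 7 days to be monitored for adverse events". Of the question put on these calls it says: "This will be an open question that will be recorded prospectively for each subject".

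**Day 30 and day 90 (section 10, second item 4).** Besides the neurologic scales, "patients will be queried at this time as to whether they experienced any nausea, vomiting, flushing, and itchiness, wheezing or difficulty breathing", with the recall period "between the time of their discharge and the reevaluation". The open question is not mentioned. On timing, "the 30 day follow up will have a tolerance range +/- 3 days and the 90 day follow up will permit +/- 10 day window".

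**Serious events (section 10(j), definitions).** The list includes "Bleeding requiring an intervention", hemorrhagic conversion, neurologic worsening on the NIHSS at four-hourly assessments, and death.

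**Purpose.** The Lay Summary (section 5) says the trial will also look at "whether there was any benefit or harm to the subjects over the time course of the study".

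**The concern.** The six symptoms are acute reactions to a 20-hour infusion, and weeks later they are the events least likely to be due to it. Item 3 already treats that list as too narrow on its own, which is why it adds the open question in hospital. The day-30 and day-90 visits keep the narrow list and drop the broad question, and these visits cover the longest part of follow-up.

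At stake is the late safety comparison. Every subject who attends is asked about mild symptoms. A bleed treated at another hospital in week 6 reaches the data only if someone happens to find it or mention it. A late safety table with few serious events could then reflect how they were collected rather than their absence.

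**Working it through.** The plan states no figure on this point, so there is none to reproduce. The check has three steps.

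**1. Which adverse-event question is written at each contact**

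| Contact | Open question | Six-symptom list |
|---|---|---|
| In hospital, four-hourly (item 3; 10(j)) | yes | yes |
| Calls at 24 hours and 3 days after discharge, and at 7 days | yes | not written |
| Day-30 and day-90 visits | not written | yes |
| Calls after a transfer or missed visit (item 7) | not written | not written |

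The list does contain six items: nausea, vomiting, flushing, itchiness, wheezing, difficulty breathing.

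**2. How much of follow-up has no open question scheduled**

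Let F be the length of follow-up in days, T the day of the last open question, and L the length of stay counted from enrollment. The share is (F − T)/F. F = 90 comes from the protocol. L is not given, so stays of up to 21 days are assumed. The protocol does not say whether the 7 days run from enrollment or from discharge.

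- From enrollment, T = 7: (90 − 7)/90 = 83/90 = 92%. This needs a stay of at most 4 days, because otherwise the call 3 days after discharge (day L + 3) comes later than day 7. With L = 21, T = 24 and the share is 66/90 = 73%.
- From discharge, T = L + 7:
  - L = 3: 80/90 = 89%
  - L = 14: 69/90 = 77%
  - L = 21: 62/90 = 69%

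The range over 90 days is therefore 69% to 92%. The ±10-day window on the last visit moves the ends only a little: T = 7 gives 73/80 = 91% to 93/100 = 93%, and T = 28 gives 52/80 = 65% to 72/100 = 72%. Most of follow-up lies after the last open question on every reading tried.

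**3. What else could find a late event**

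- *Neurologic scales at both visits.* NIHSS, modified Rankin, Glasgow Outcome Scale and Barthel Index measure status, and death is a level of the modified Rankin and Glasgow scales. The examiner is blinded to earlier scores, the listed worsening event is tied to four-hourly assessments, and no rule turns a worse late score into a reported event.
- *Record review by the study team (section 10; 10(f)).* Its stated aim is to obtain the visit results and notes.
- *Safety Monitor's record review (10(j)).* It runs through the trial, but no interval is given and nothing says it reaches other hospitals' records. Item 7 itself foresees transfers to outside hospitals.
- *MRI at 3 months (item 6).* The listed readings are stroke type, edema, volume change and gliosis. Hemorrhage is not among them, and a brain MRI cannot show bleeding elsewhere in the body.
- *Instruction to return (item 5).* This relies on the subject coming back, for worsening or new neurologic symptoms.
- *Calls after transfer or a missed visit (item 7).* At most three calls in a week, with no adverse-event question written. Section 10(b) allows for 25% dropout or loss to follow-up.
- *Volunteered reports.* The visit query is put to patients, and no caregiver is mentioned. Yet 39 of the 117 planned subjects have an NIHSS of 21 to 42.

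**The case against.** A reader might infer that late adverse events are sought only through the six symptoms, or that late neurologic worsening goes unmeasured. The documents do not support either. The query is expressly additional to a blinded examination with four scales, the 90-day NIHSS is the primary endpoint, and the routes in step 3 exist. Neurologic worsening as listed is also an acute-phase event, defined on four-hourly scores.

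A reader might also want a count of missed serious events. The documents give no late event rate. Days without an open question measure exposure to the gap, not events lost.

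Four further points deserve weight:

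- Hemorrhagic conversion is diagnosed by imaging or a clinician, so asking the patient is a weak detector. This is true, but a prompt about hospital care or a reported brain hemorrhage leads to the record that holds the diagnosis.
- Concentrating open questions around a 20-hour infusion is defensible, and section 10(e) lists no safety endpoint. That lowers the priority. It does not explain why the visits ask weeks later about the infusion symptoms.
- Item 7 provides telephone contact for subjects who are transferred or miss a visit. That contact helps only if the adverse-event question is part of it.
- Section 10(g) refers to attached data collection sheets that are not in the public file and might already carry an event or hospitalization field. If so, the protocol text should be brought into line with them. They cannot be assumed to override it.

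**Conclusion.** The point holds as a gap in how late harm is collected. No open adverse-event question is scheduled for about 69% to 92% of the 90 days. The one adverse-event question written for days 30 and 90 does not reach bleeding that needs intervention, hemorrhagic conversion or care given elsewhere. Neurologic status and death are covered by the scales. The other routes are unscheduled, read for other purposes, or depend on the subject.

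The range rests on two assumptions: where the 7 days start, and a stay of up to 21 days. The conclusion rests on the protocol text as published, without the attached data sheets. No sample size, power figure or primary analysis is affected. This is a cheap improvement, not a defect that undermines the trial's main result.

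**What to change.** In section 10, second item 4 (day-30 and day-90 visits), and in the matching text of 10(f):

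- Keep the six-symptom query and add the open question already used on the telephone calls.
- Add yes/no prompts for bleeding that needed intervention, recurrent stroke or intracranial hemorrhage, and any emergency visit or hospital stay at any facility since the last contact.
- Put the questions to a caregiver when the subject cannot answer.
- Use the same questions in the item 7 calls for transferred subjects and missed visits.
- State whether the 7-day call is counted from enrollment or from discharge.
- Tabulate events after the 7-day call by arm.

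The cost is a wording change, a few lines on the follow-up data sheets, a few more minutes per visit, and more unrelated events to log. No visit is added.
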